N= number of subjects with at least one RSV infection (symptomatic or asymptomatic)

n/% = number/percentage of subjects reporting at least one RSV hospitalization

95%CI= Exact 95% confidence interval; LL = lower limit, UL = upper limit

Template 41 Number and percentage of subjects reporting the RSV infection of different severity (based on WHO case definition) by number of events experienced between vaccination dose 1 up to end of <first, second> RSV season for pooled RSV 1D, RSV 2D and Comparator/Placebo group <Exposed Set, Exposed Set with negative RSV baseline status>

Characteristics	Categories	<Each group> N=xx				
		n	%	95% CI	LL	UL
RSV infection-symptomatic or asymptomatic*	0					
	1					
	2					
RSV-RTI	0					
	1					
RSV-LRTI	0					
	1					
	2					
RSV-Severe LRTI	0					
	1					
RSV-very severe LRTI	0					
	1					
All cause LRTI	0					
	1					
	2					
	3					
RSV hospitalization\$	0					
	1					
	2					
	3					

Short group label = long group label

N = number of subjects in each group

n = number of subjects in a given category

% = $100 * n / N$

LL, UL for percentage = Exact 95% Lower and Upper confidence limits

Please note – Single episode can be considered in multiple category depending on the symptom experienced

* Association to RSV based on central testing only for asymptomatic visit (no local test available)

\$Confirmed RSV infection and hospitalized for acute medical condition

Template 42 Number and percentage of RSV infections and associated disease severity (based on WHO case definition) and relative risk from vaccination dose 1 up to end of <first, second> RSV season for pooled RSV 1D, RSV 2D and Comparator/Placebo group <Exposed Set, Exposed Set with negative RSV baseline status>

Categories	<Each Group> N =		Relative risk (RSV1D vs Comparator/Placebo)				Relative risk (RSV2D vs Comparator/Placebo)			
			95% CI		95% CI				95% CI	
	n	%	LL	UL	Values	LL	UL	Values	LL	UL
RSV asymptomatic (Excluding RSV-RTI, LRTI, RSV-severe LRTI or RSV-very severe LRTI)										
RSV RTI (Excluding LRTI, RSV-severe or very severe LRTI)										
RSV LRTI (Excluding RSV-severe or very severe LRTI)										
RSV-severe LRTI (Excluding RSV-very severe LRTI)										
RSV-very severe LRTI										

Short group label = long group label

* Association to RSV based on central testing only for asymptomatic visit (no local test available)

N = number of RSV positive samples in each group

n** = number of cases in each category

n/% = number/percentage of cases in each category

95%CI= Exact 95% confidence interval; LL = lower limit, UL = upper limit

Please note – Single episode is considered in single category of highest severity based on the symptom experienced

Template 43 Number and percentage of RSV infections (based on WHO case definition) requiring hospitalization between vaccination dose 1 up to end of <first, second> RSV season for pooled RSV 1D, RSV 2D and Comparator/Placebo group <Exposed Set, Exposed Set with negative RSV baseline status>

Categories	Group N =				Total N =					
			95% CI				95% CI			
	n**	n	%	LL	UL	n**	N	%	LL	UL
RSV RTI*(Excluding LRTI, severe or very severe LRTI)										
RSV LRTI (Excluding severe or very severe LRTI)										
RSV-severe LRTI (Excluding very severe LRTI)										
RSV-very severe LRTI										

Short group label = long group label

N = number of RSV infections in each group

n** = number of cases in each category

n/% = number/percentage of subjects reporting at least once the case

95%CI= Exact 95% confidence interval; LL = lower limit, UL = upper limit

Template 44 Descriptive statistics of viral load calculated on all qRT-PCR confirmed RSV infection episodes with varying disease severity (based on WHO case definition) from vaccination dose 1 up to end of <first, second> RSV season for pooled RSV 1D, RSV 2D and Comparator/Placebo group <Exposed Set, Exposed Set with negative RSV baseline status>

Symptoms	Parameters	Group N=		
		Value	LL	UL
RSV asymptomatic* (Excluding RSV-RTI, RSV-LRTI, RSV-severe LRTI or RSV-very severe LRTI)	n			
	GM			
	95% CI			
	SD			
	Q1			
	Median			
	Q3			
	Min/Max			
RSV RTI (Excluding RSV-LRTI, RSV-severe LRTI or RSV-very severe LRTI)				
RSV LRTI (Excluding RSV-severe or RSV-very severe LRTI)				
RSV-severe LRTI (Excluding RSV-very severe LRTI)				
RSV-very severe LRTI				
RSV hospitalization\$				

Short group label = long group label

N = number of RSV infections episodes in each group

n= Number of events in each category

SD=Standard Deviation

Q1 and Q3 = 1st and 3rd quantiles

Min/Max = Minimum/Maximum

GM = Geometric mean

LL, UL for GM = Exact 95% Lower and Upper confidence limits

Total RSV viral load computed as RSV A Viral load + RSV B Viral load

* Association to RSV based on central testing only for asymptomatic visit (no local test available)

\$Confirmed RSV infection and hospitalized for acute medical condition

Please note: each episode for a subject is considered to be independent. We may have multiple swab for one episode.

We have considered the swab with maximum viral load from one episode for the table

Please note – Except for RSV hospitalization, single episode is considered in single category of highest severity based on the symptom experienced

Please check:- To check for cases where asymptomatic swab has been taken but the subject hasve symptoms of RTI or LRTI. In this case, asymptomatic is also considered as RSV RTI/LRTI and maximum viral load of all the episode should be considered.

Template 45 Descriptive statistics of maximum viral load per subjects based on qRT-PCR confirmed episode with varying disease severity (based on WHO case definition) from vaccination dose 1 up to end of <first, second> RSV season for pooled RSV 1D, RSV 2D and Comparator/Placebo group <Exposed Set, Exposed Set with negative RSV baseline status>

Symptoms	Parameters	Each Group N=		
		95% CI		
RSV asymptomatic* (Excluding RSV-RTI, RSV-LRTI, RSV-severe LRTI or RSV-very severe LRTI)	n			
	GM			
	95% CI			
	SD			
	Q1			
	Median			
	Q3			
RSV RTI (Excluding RSV-LRTI, RSV-severe or RSV-very severe LRTI)	Min/Max			
	...			
RSV LRTI (Excluding RSV-severe or RSV-very severe LRTI)	...			
RSV-severe LRTI (Excluding RSV-very severe LRTI)	...			
RSV-very severe LRTI	...			
RSV hospitalization\$...			

Short group label = long group label

N = number of RSV positive subjects in each group

n= Number of subjects in each category

SD=Standard Deviation

Q1 and Q3 = 1st and 3rd quantiles

Min/Max = Minimum/Maximum

GM = Geometric mean

LL, UL for GM = Exact 95% Lower and Upper confidence limits

Total RSV viral load computed as RSV A Viral load + RSV B Viral load

Please note: Except of RSV hospitalization, the subject has been considered only once in one of the category based on the maximum severity of event experienced

* Association to RSV based on central testing only for asymptomatic visit (no local test available)

\$Confirmed RSV infection and hospitalized for acute medical condition

Template 46 Frequency of multiple respiratory pathogen for qRT-PCR confirmed RSV-RTI episodes from vaccination dose 1 up to end of <first, second> RSV season for pooled RSV 1D, RSV 2D and Comparator/Placebo groups <Exposed Set, Exposed Set with negative RSV baseline status>

Categories	Group N =				Total N =			
			95% CI				95% CI	
	n	%	LL	UL	n	%	LL	UL
Influenza Virus A/California/7/2009(H1N1)								
Adenovirus								
Human Coronavirus OC43								
Human Coronavirus 229E								
Human Coronavirus NL63								
Human Coronavirus HKU1								
Enterovirus + Rhinovirus								
Influenza Virus A								
Influenza Virus B								
Influenza Virus A (H1N1)								
Influenza Virus A (H3N2)								
Human bocavirus								
Human metapneumovirus								
Parainfluenza virus 1								
Parainfluenza virus 2								
Parainfluenza virus 3								
Parainfluenza virus 4								

Short group label = long group label

N = number of qRT-PCR confirmed RSV-RTI infection episodes in each group

n = number of episodes in a given category

% = $100 * n / N$

LL, UL for percentage = Exact 95% Lower and Upper confidence limits

Template 47 Frequency of multiple respiratory pathogen for confirmed LRTI episodes from vaccination dose 1 up to end of <first, second> RSV season for pooled RSV 1D, RSV 2D and Comparator/Placebo groups <Exposed Set, Exposed Set with negative RSV baseline status>

Categories	Group N =				Total N =			
	95% CI				95% CI			
	n	%	LL	UL	n	%	LL	UL
Respiratory syncytial virus								
Influenza Virus A/California/7/2009(H1N1)								
Adenovirus								
Human Coronavirus OC43								
Human Coronavirus 229E								
Human Coronavirus NL63								
Human Coronavirus HKU1								
Enterovirus + Rhinovirus								
Influenza Virus A								
Influenza Virus B								
Influenza Virus A (H1N1)								
Influenza Virus A (H3N2)								
Human bocavirus								
Human metapneumovirus								
Parainfluenza virus 1								
Parainfluenza virus 2								
Parainfluenza virus 3								
Parainfluenza virus 4								

Short group label = long group label

N = number of confirmed LRTI infection episodes in each group

n = number of episodes in a given category

% = $100 * n / N$

LL, UL for percentage = Exact 95% Lower and Upper confidence limits

Template 48 Listing of RSV-RTI cases identified according to WHO case definitions from vaccination dose 1 up to end of second RSV season <Exposed Set, Exposed Set with negative RSV baseline status>

Group No.	Sub No.	Sex	Age at episode(mo nth)	Count	Surveill ance type	Epis ode nb	Do se nb	Do se nb	On set nb. day	Sp O2	Respir atory rate	Cen tral test	Cen tral test	RSV -RTI A	RSV -RTI B	RSV -LRT I	Sev ere -LRT I	Sev ere -LRT I	RSV very sev ere -LRT	Hospita lization	RVP result
																	Yes/ No	Yes/ No	Yes/ No	Yes/ No	

Short group label = long group label

Template 49 Listing of RSV-RTI requiring hospitalization and type of inpatient facility required from vaccination dose 1 up to end of second RSV season <Exposed Set, Exposed Set with negative RSV baseline status>

Group	Sub No.	Sex	Age at episode (month)	Country	Classification of episode per WHO*	Total days hospitalized	No. of days of monitoring or nursing	No. of days of strict or intravenous fluids given	No. of days oxygen administered	No. of days respiratory support given	No. of days mechanical ventilation given	No. of days child kept in hospital	No. of days in paediatrics intensive care unit	RVP	Pathogen identified in RVP
														Yes/No	

Short group label = long group label

*subject will be classified per maximum severity experienced

Template 50 Number and percentage of subjects with highest associated severity of RSV infection (based on WHO case definition) from vaccination dose 1 up to <first, second> RSV season for pooled RSV 1D, RSV 2D and Comparator/Placebo groups <Exposed Set, Exposed Set with negative RSV baseline status>

Categories	Group N =				Total N =			
	n**	n	%	95% CI	n**	n	%	95% CI
No Infection								
RSV asymptomatic (Excluding RSV-RTI, RSV-LRTI, RSV-severe LRTI or RSV-very severe LRTI)								
RSV RTI (Excluding RSV-LRTI, RSV-severe or very severe LRTI)								
RSV LRTI (Excluding RSV-severe or very severe LRTI)								
RSV-severe LRTI (Excluding RSV-very severe LRTI)								
RSV-very severe LRTI								

Short group label = long group label

N = number of subjects in each group

n** = number of cases in each category

n/% = number/percentage of subjects reporting at least once the case

95%CI= Exact 95% confidence interval; LL = lower limit, UL = upper limit

Please note – Single episode can be considered in single category depending on the highest severity symptom experienced

Template 51 Number and percentage of subjects reporting the RSV infection of maximum severity (based on WHO case definition) by number of events experienced between vaccination dose 1 up to end of <first, second> RSV season for pooled RSV 1D, RSV 2D and Comparator/Placebo groups <Exposed Set, Exposed Set with negative RSV baseline status >

Characteristics	Categories	Total			95% CI	
		N	n	%	LL	UL
RSV asymptomatic (Excluding RSV-RTI, RSV-LRTI, RSV-severe LRTI or RSV-very severe LRTI)	0					
	1					
	2					
RSV-RTI (Excluding RSV-LRTI, RSV severe or very severe LRTI)	0					
	1					
RSV-LRTI (Excluding RSV severe or very severe LRTI)	0					
	1					
RSV-Severe LRTI Excluding RSV very severe LRTI)	0					
	1					
RSV-very severe LRTI	0					
	1					

Short group label = long group label

N = number of subjects in each group

n = number of subjects in a given category

% = $100 * n / N$

LL, UL for percentage = Exact 95% Lower and Upper confidence limits

Please note – Single episode will be considered in single category depending on the maximum severity experienced

Template 52 Number and percentage of subjects with <anti-RSV A antibody titre, anti-RSV F concentration> equal to or above <cut-off ><unit> and gm<t,c> for pooled RSV 1D, RSV 2D and Comparator/Placebo> groups – by RSV baseline status (<Adapted>PPS of immunogenicity at <Day X, end of 1st RSV season>)

Antibody off	Time point	Cut- <RSV+ve>	<Each group>								
			<RSV-ve>				95% CI				
			N	n	value	95% CI	N	n	value	95% CI	
		<Antibody 1> <Time point 1> <Cut-%>=<cut-off 1> off 1> <unit>	xxx	xxx	xx.x	xx.x	xx.x	xxx	xxx	xx.x	xx.x
		GM<T,C>	xxx		xx.x	xx.x	xx.x	xxx		xx.x	xx.x
										xx.x	

Short group label = long group label

GMT/C = geometric mean antibody titer/concentration

N = Number of subjects with available results

n/% = number/percentage of subjects with titer/concentration equal to or above specified value

95% CI = 95% confidence interval; LL = lower limit, UL = upper limit

PRE= Pre-vaccination

D31 = Post-vaccination at Day 31

D61 = Post-vaccination at Day 61

RSV1S = End of 1st RSV transmission season

RSV+ve = Subjects are RSV positive at baseline

RSV-ve = Subject are RSV negative at baseline

Template 53 Distribution of <RSV-A neutralising antibody titre, RSV-F antibody concentration> for pooled RSV 1D, RSV 2D and Comparator/Placebo> groups – by RSV baseline status(<Adapted>PPS for immunogenicity <at Day X, end of 1st RSV season>)

Antibody	Time point	Cut-off	<Each group>											
			<RSV+ve>						<RSV-ve>					
			95% CI			95% CI			95% CI			95% CI		
			N	n	value	LL	UL	N	n	value	LL	UL		
<Antibody 1>	<Time point 1>	<cut-off 1>	xxx	xxx	xx.x	xx.x	xx.x	xxx	xxx	xx.x	xx.x	xx.x	xx.x	xx.x
		>=cut-off 2	xxx	xxx	xx.x	xx.x	xx.x	xxx	xxx	xx.x	xx.x	xx.x	xx.x	xx.x
		>=cut-off 3	xxx	xxx	xx.x	xx.x	xx.x	xxx	xxx	xx.x	xx.x	xx.x	xx.x	xx.x
	<Time point 2>	<cut-off 1>	xxx	xxx	xx.x	xx.x	xx.x	xxx	xxx	xx.x	xx.x	xx.x	xx.x	xx.x
		>=cut-off 2	xxx	xxx	xx.x	xx.x	xx.x	xxx	xxx	xx.x	xx.x	xx.x	xx.x	xx.x
		>=cut-off 3	xxx	xxx	xx.x	xx.x	xx.x	xxx	xxx	xx.x	xx.x	xx.x	xx.x	xx.x

Short group label = long group label

N = number of subjects with available results

n/% = number/percentage of subjects with <titer, concentration> within the specified criterion

<95>% CI = <95>% confidence interval; LL = Lower Limit, UL = Upper Limit

PRE= Pre-vaccination

D31 = Post-vaccination at Day 31

D61 = Post-vaccination at Day 61

RSV1S = End of 1st RSV transmission season

RSV+ve = Subjects are RSV positive at baseline

RSV-ve = Subject are RSV negative at baseline

Template 54 Number and percentage of subjects with <anti-RSV A antibody titre, anti-RSV F concentration> equal to or above <cut-off><unit> and GMR for pooled RSV 1D, RSV 2D and Comparator/Placebo> groups – by RSV baseline status (PPS of immunogenicity at <Day X, End of 1st RSV season>)

Antibody Cut-off	Time point	<Each group>											
		<RSV+ve>						<RSV-ve>					
		95% CI		95% CI									
		N	n	value	LL	UL	N	n	value	LL	UL		
<Antibody 1>	<Time point 1>	%>=<cut-off 1> <unit>	xxx	xxx	xx.x	xx.x	xx.x	xxx	xxx	xx.x	xx.x	xx.x	
<Cut-off 1>		GMC/T		xxx		xx.x	xx.x	xx.x	xxx		xx.x	xx.x	xx.x
		Visit comparison / baseline											
		GMR		xxx	xx.x	xx.x	xx.x	xxx		xx.x	xx.x	xx.x	

Short group label = long group label

GMT = geometric mean antibody titer

N = Number of subjects with available results at the two considered time points

95% CI = 95% confidence interval; LL = Lower Limit, UL = Upper Limit

PRE= Pre-vaccination

D31 = Post-vaccination at Day 31

D61 = Post-vaccination at Day 61

RSV1S = End of 1st RSV transmission season

RSV+ve = Subjects are RSV positive at baseline

RSV-ve = Subject are RSV negative at baseline

Template 55 Descriptive statistics of <anti-RSV A neutralizing antibody titre, anti-RSV F antibody concentration> at pre-vaccination, Day <31, 61, > <and end of 1st RSV transmission season> for pooled RSV 1D, RSV 2D and Comparator/Placebo> groups – by RSV baseline status (<Adapted> PPS for immunogenicity)

Visit	Characteristics	Each Group N=XXXX	
		RSV+ve N=XXXX	RSV-ve N=XXXX
PRE	N with data Mean SD Q1 Median Q3 95% CI		
D31	...	(xx.x ; xx.x)	(xx.x ; xx.x)
D61	...		
RSV1S	...		

Short group label = long group label

N = total number of subjects

N with data = number of subjects with available results

Value = value of the considered parameter

SD = standard deviation

Q1 and Q3 = 1st and 3rd quantiles

LL, UL = Exact 95% Lower and Upper confidence limits

PRE= Pre-vaccination

D31 = Post-vaccination at Day 31

D61 = Post-vaccination at Day 61

RSV1S = End of 1st RSV transmission season

RSV+ve = Subjects are RSV positive at baseline

RSV-ve = Subject are RSV negative at baseline

Template 56 Summary of subjects by unsolicited adverse event category with onset within 30 days of first and second vaccination (Exposed Set)

	<Group 1> N=XXXX				<Group 2> N=XXXX			
			95% CI				95% CI	
	n	%	LL	UL	n	%	LL	UL
At least one unsolicited adverse event	xxx	xx.x	xx.x	xx.x	xxx	xx.x	xx.x	xx.x
At least one related unsolicited adverse event	xxx	xx.x	xx.x	xx.x	xxx	xx.x	xx.x	xx.x
At least one grade 3 unsolicited adverse event	xxx	xx.x	xx.x	xx.x	xxx	xx.x	xx.x	xx.x
At least one grade 3 related unsolicited adverse event	xxx	xx.x	xx.x	xx.x	xxx	xx.x	xx.x	xx.x
At least one medically attended unsolicited adverse event	xxx	xx.x	xx.x	xx.x	xxx	xx.x	xx.x	xx.x

Any adverse event = at least one adverse event experienced (regardless of the MedDRA Preferred Term)

N = number of subjects with at least one administered vaccination

n/% = number/percentage of subjects reporting the adverse event at least once

95% CI = exact 95% confidence interval; LL = Lower Limit, UL = Upper Limit

Template 57 Number and percentage of subjects with at least one RSV-RTI progressing to RSV-LRTI, RSV-severe LRTI, RSV-very severe LRTI and RSV hospitalization from vaccination dose 1 up to end of <first, second> RSV season for pooled RSV 1D, RSV 2D and Comparator/Placebo groups <ES, Exposed Set with negative RSV exposure status>

Categories	<each group> N =				Total N =			
			90% CI				90% CI	
	n	%	LL	UL	n	%	LL	UL
RSV-LRTI								
RSV-severe LRTI								
RSV-very severe LRTI								
RSV hospitalization*								

<Blinded = Blinded group>

<RSV 1D = Pooled 1D RSV>

<RSV 2D = Pooled 2D RSV>

<COMP_PLB = Pooled comparator or placebo>

* Confirmed RSV infection and hospitalized for acute medical condition

N = number of subjects with at least one RSV-RTI infection

n/%= number/percentage of subjects reporting at least once the symptom

90%CI= Exact 90% confidence interval; LL = lower limit, UL = upper limit

Please note – Single episode is considered in single category of highest severity based on the symptom experienced

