4. ANALYSIS SETS

4.1. Definition

4.1.1. Exposed Set

The Exposed Set (ES) will include all subjects with at least one study vaccine administration documented.

- A safety analysis based on the ES will include all vaccinated subjects.
- An immunogenicity analysis will be conducted on the ES and will include all vaccinated subjects for whom immunogenicity data are available.

The ES analysis will be performed per treatment actually administered at Dose 1

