5.3.2.3. Solicited Adverse Events

All analyses will be based on the ‘as treated’ analysis set. Solicited adverse events will be reported daily during the 7-day (from Day 1 to Day 7) follow up period after each vaccination, using structured diaries.

In order to summarize the data, the maximum intensity of local injection site redness/swelling (in mm) and fever (in $^{\circ}\text{C}$) will be categorized as follows:

Grading	Redness/swelling	Fever
0:	None	$< 38.0^{\circ}\text{C}$ (100.4°F)
1:	< 5 mm	$\geq 38.0^{\circ}\text{C}$ (100.4°F) - $\leq 39.0^{\circ}\text{C}$ (102.2°F)
2:	$> 5 - \leq 20$ mm	$> 39.0^{\circ}\text{C}$ (102.2°F) - $\leq 40.0^{\circ}\text{C}$ (104.0°F)
3:	> 20 mm	$> 40.0^{\circ}\text{C}$ (104.0°F)

Fever is defined as temperature $\geq 38.0^{\circ}\text{C} / 100.4^{\circ}\text{F}$ (regardless of the location of measurement). The preferred location for measuring temperature in this study will be the oral cavity. Body temperature will also be summarized by 0.5°C increments as follows: $\geq 38.0, >38.5, >39.0, >39.5, >40.0^{\circ}\text{C}$.

For each of the time points or time intervals presented in the summaries, only subjects with at least one plausible observation (i.e., any non-missing values but excluding “Not done/unknown” and implausible values) for the solicited adverse events in the interval of interest will be considered. Subjects without plausible data (i.e. missing values or reported as “Not done/unknown” and implausible values) will be removed from the denominator to prevent a downward bias (towards zero).

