5.4. Analysis of RTI and LRTI

5.4.1. Analysis of RTI and LRTI planned in protocol

The primary analysis will be performed on the ES of subjects with a negative RSV exposure status (at screening based on in-stream baseline serological testing) in the pooled single dose RSV vaccine group, the pooled two dose RSV vaccine group, and the pooled comparator group separately for first and second RSV seasons and overall. A similar analysis will be performed on the entire ES. As primary analysis, the assessment of RSV infection will be performed using the quantitative RT-PCR according to standardized case definitions (see Table 6 of the SAP) based on the available WHO case definitions.

The number of RSV infections within each group and the maximum disease severity of the event will be tabulated. The rate (with 95% CI) of RSV-RTI and RSV-LRTI and infections progressing to hospitalization will be evaluated for each of the three pooled groups.

The rate of very severe RSV-LRTI among RSV infected infants with a negative RSV exposure status (at screening based on in-stream baseline serological testing) from first vaccination (Day 1) up to the end of the first RSV transmission season will be estimated as well as 95% one-sided lower CI.

The proportion and the relative risk of subjects with at least one RSV-associated RTI (with 95% CI) between each of two pooled RSV vaccine groups and the pooled control group will be calculated for both the cohort of subjects with a negative RSV exposure status (at screening based on in-stream baseline serological testing) on the ES and on the entire ES. The same descriptive analysis will be performed for subjects with at least one RSV-associated LRTI and those with at least one RSV-associated severe LRTI.

Descriptive analyses (mean, median, min, max) of viral load assessed by the quantitative RT-PCR (RSV-A/B) of all cases as listed in Table 6 of the SAP will be tabulated by case category. This analysis will also be done on the three pooled groups.

The incidence rate of all cases as listed in Table 6 of the SAP (with 95% CI) will be calculated by the three pooled groups. The same descriptive analysis will be performed for all cause LRTI and all cause severe LRTI. These will also be presented for each viral etiology identified by the multiplex PCR.

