Template 37 Reverse cumulative distribution curves for anti-RSV-A neutralising antibody titres in each group at baseline and <Day 31, Day 61, End of first RSV season> for pooled RSV 1D, RSV 2D and Comparator/Placebo group <PPS for analysis of immunogenicity at <Day X, End of 1st RSV season>

Short group label = long group label

Template 38 Individual results of anti-RSV-A neutralising antibody titre at Day <61/end of first RSV season> versus pre-vaccination in <each pooled <RSV 1D, RSV 2D> group> and Comparator/placebo group> (PPS for analysis of immunogenicity at <Day X>)

Note: This graph is provided as an example. The same graph will be generated for each assay and each timepoint separately (Days 61, end of first RSV season)

Template 39 Number and percentage of subjects with at least one RSV infection, RSV-RTI, RSV-LRTI, RSV-severe LRTI, RSV-very severe LRTI, All-cause LRTI and RSV hospitalization (based on WHO case definition) from vaccination dose 1 up to end of <first, second> RSV season for pooled RSV 1D, RSV 2D and Comparator/Placebo group (<Exposed Set, Exposed Set with a negative RSV exposure status>)

Categories	<each group> N =				Total N =			
			95% CI				95% CI	
	n	%	LL	UL	n	%	LL	UL
No infection								
RSV-infection symptomatic or asymptomatic*								
RSV-RTI								
RSV-LRTI								
RSV-severe LRTI								
RSV-very severe LRTI								
All-cause LRTI								
RSV hospitalization**								

Short group label = long group label

* Association to RSV based on central testing only for asymptomatic visit (no local test available)

** Confirmed RSV infection and hospitalized for acute medical condition

N = number of subjects with at least one administered dose

n/% = number/percentage of subjects reporting at least once the symptom

95%CI= Exact 95% confidence interval; LL = lower limit, UL = upper limit

Template 40 Proportion of subjects with at least one RSV hospitalization over the number of subjects with at least one RSV infection (symptomatic or asymptomatic*) from vaccination dose 1 up to end of <first, second> RSV season for pooled RSV 1D, RSV 2D and Comparator/Placebo group <Exposed Set, Exposed Set with negative RSV baseline status>

Symptom	<each group> N=			
			95 % CI	
	n	%	LL	UL
RSV hospitalization**				

Short group label = long group label

* Association to RSV based on central testing only for asymptomatic visit (no local test available)

** Confirmed RSV infection and hospitalized for acute medical condition

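### Templates 39, 41 and 50 keep infants lost to follow-up in the denominator with no category except uninfected, so the crude RSV percentages understate full-season risk

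*SAP*

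**What the plan says.** - **Analysis set.** Section 4.1.1 asks only for one documented dose: "The Exposed Set (ES) will include all subjects with at least one study vaccine administration documented". Section 5.4.1 analyses RTI and LRTI on this set and on its RSV-negative subset.
- **Template 39** (Section 13) covers Dose 1 to the end of the first or second season. Its denominator is "N = number of subjects with at least one administered dose" and its numerator is "n/% = number/percentage of subjects reporting at least once the symptom". Its rows are no infection and the case categories.
- **Templates 41 and 50** use "N = number of subjects in each group". Template 41 has a zero-event line for each case type, and Template 50 has a no-infection row.
- **Incidence rate.** Section 5.4.1 states: "The incidence rate of all cases as listed in Table 6 of the SAP (with 95% CI) will be calculated by the three pooled groups". It defines no person-time, and no template shows any.
- **Contrast.** Section 5.4.1 also plans "The proportion and the relative risk of subjects with at least one RSV-associated RTI (with 95% CI"), each pooled RSV group against pooled control, and repeats this for LRTI and severe LRTI.
- **Missing follow-up.** Sections 5.4, 9.2 and 10.1.2 contain no censoring, minimum-surveillance or imputation rule for RSV outcomes. Section 10.1.2.2 leaves missing laboratory results unreplaced. Withdrawals appear in the disposition and discontinuation outputs but are not carried into the RSV tables.
- **Status of the templates.** Sections 10 and 10.2 say that no separate table specification was prepared, so the Section 13 templates are the output specification.

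**The concern.** Dose 1 is given before the first RSV season and the study lasts about 24 months. An infant can be dosed, leave, and never be under in-season surveillance. Asymptomatic infection is sought by monthly swabs during the season, so an infant who has left has an unknown status for that period, not a negative one. The same holds, in the tables running to the end of the second season, for an infant lost between seasons.

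With every dosed infant in the denominator and no row for unknown status, these infants dilute the percentage. RSV-RTI, RSV-LRTI, severe and very severe RSV-LRTI through each season are secondary endpoints, and their occurrence would be reported too low. If loss also differed between groups, the relative risk of Section 5.4.1 would move in either direction.

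**Working it through.** The SAP gives no dropout rate, attack rate or expected percentage, so there is no figure of its own to reproduce. The check asks how far the tabulated percentage falls below the true full-season risk under stated assumptions.

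**Inputs**
- Group size: 50 per pooled group (Table 2 target).
- Denominator: all dosed infants (Template 39).
- Assumed: true risk p = 30%; dropout d = 5%, 10% or 20%; f = share of the season's cumulative hazard observed before loss, with f = 0 for loss before the season and f = 0.5 for mid-season loss.

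**Tabulated percentage**

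p_obs = (1 − d) × p + d × [1 − (1 − p)^f]

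For f = 0 the second term vanishes. For f = 0.5 and p = 30% the bracket is 1 − √0.70 = 0.1633.

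| Dropout | Loss before season | Loss at mid-season |
|---|---|---|
| 5% | 0.95 × 30% = 28.5% | 28.5% + 0.05 × 16.33% = 29.3% |
| 10% | 0.90 × 30% = 27.0% | 27.0% + 0.10 × 16.33% = 28.6% |
| 20% | 0.80 × 30% = 24.0% | 24.0% + 0.20 × 16.33% = 27.3% |

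**One group in counts.** Suppose 50 are dosed, 10 are lost before the season, and 12 of the remaining 40 are infected.
- As the template is written: 12/50 = 24.0% (exact 95% CI 13.1 to 38.2), no infection 38/50 = 76%.
- Among infants under surveillance: 12/40 = 30.0% (16.6 to 46.5), no infection 28/40 = 70%.

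If the 10 are censored before the season, a Kaplan-Meier estimate gives 1 − 28/40 = 30.0%, the assumed true risk, provided that loss is unrelated to risk.

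**Subject-level relative risk, true value 1.0**
- Equal dropout with the same timing: 1.00.
- 20% in an RSV group, 4% in control, loss before the season: 0.80/0.96 = 0.83. Reversed: 0.96/0.80 = 1.20.
- The same rates with half of the risk seen before loss: (1 − 0.5 × 0.20)/(1 − 0.5 × 0.04) = 0.90/0.98 = 0.92. Reversed: 1.09. Taking half of the cumulative hazard at 30% risk instead gives 27.27/29.45 = 0.93 and 1.08.

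**True relative risk 2.0** (30% against 15%) with 10% dropout in both groups: 2.00 for loss before the season and 2.005 for mid-season loss.

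**Measures with another denominator**
- Section 6 criterion, Template 40: RSV-infected infants.
- Template 57: infants with RSV-RTI.
- Template 42, the only template showing a relative risk: RSV-positive samples.

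An infant lost without a detected infection enters neither numerator nor denominator of these. The mismatch between Template 42 and the subject-level relative risk of Section 5.4.1 is a separate matter.

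**The case against.** Several points on the other side stand.

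- **Enhanced disease.** A reader might infer that dropout dilutes the SAP's criterion for enhanced disease. It does not: the 80% threshold in Section 6 applies to very severe RSV-LRTI among infected infants.
- **Contrast.** A reader might infer that the vaccine-control comparison is biased as such. It is not: equal, similarly timed loss leaves the relative risk almost unchanged, and Templates 39, 41 and 50 show no relative risk. Only the subject-level sentence in Section 5.4.1 is exposed. Families stay blinded to the last visit (Section 7.1), which makes treatment-driven loss less likely. If both groups truly had 10% dropout, the difference in numbers lost would have SD √(2 × 50 × 0.1 × 0.9) = 3, so a gap of 8 or more infants (as in 20% against 4%) would arise in about 1% of trials. A relative risk of 0.83 at these sizes has a 95% CI of about 0.43 to 1.61, and Section 6 already calls comparisons exploratory.
- **Solicited events.** A reader might infer that the SAP contradicts itself, because Section 5.3.2.3 says that subjects without plausible data "will be removed from the denominator to prevent a downward bias (towards zero". That is an analogy only. The rule removes subjects with no plausible observation at all in the interval; one usable observation keeps a subject in. Surveillance starts after Dose 1, so most early leavers would stay in under the same rule.
- **Rare outcomes.** At an assumed 5% risk, 10% loss before the season shifts the figure from 5% to 4.5%.
- **Visibility.** Templates 2, 3 and 8 show withdrawal, contact completion and study completion by group.

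The no-infection row is also undefined, so placing lost infants there is an inference. But the tables offer no other place, and disposition tables do not correct a percentage.

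**Conclusion.** The concern holds for the crude percentages in Templates 39, 41 and 50. Under the plan as written they understate full-season risk whenever infants leave uninfected before the period ends. On the assumed figures the reported value is 0.95, 0.90 or 0.80 of the true value at 5%, 10% or 20% loss before the season, and about 0.98, 0.95 or 0.91 with mid-season loss. Infants infected before they leave still count as cases; only their later risk goes unobserved.

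For the relative risk in Section 5.4.1 the effect is conditional on unequal or differently timed loss, and the 0.83 and 1.20 figures illustrate a large imbalance, not an expected one. All sizes rest on assumed dropout and attack rates. The documents do not support a claim that the Section 6 criterion is compromised or that harm is being masked.

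The change is worth making: it is cheap, and it would also define the incidence rate that Section 5.4.1 promises.

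**What to change.** In Section 5.4.1 and Templates 39, 41 and 50:

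1. For each pooled group, add a Kaplan-Meier cumulative incidence of first event with 95% CI, censored at withdrawal or last surveillance contact. Where the category includes asymptomatic infection, the last swab is the natural censoring date. An alternative is first events per in-season surveillance person-time with exact Poisson 95% CI, which would also define the incidence rate. Person-time counted straight from Dose 1 is less suitable, because it mixes off-season and in-season time when the hazard is seasonal.
2. Keep the crude Exposed Set percentage beside it.
3. Limit the no-infection and zero-event rows to infants followed to season end, and add a row for no infection observed with incomplete follow-up. Template 51 has the same layout and should follow.
4. State which estimate the relative risk in Section 5.4.1 uses.

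The cost is SAP wording and a little programming; surveillance-visit and withdrawal data already feed planned outputs (Templates 2 and 3, Appendix Table V.A). Intervals become slightly wider, and the censored estimate assumes that loss is non-informative, which is a reason to show both figures.
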